3.1.2. SECONDARY STUDY OUTCOMES

- Proportion of participants experiencing adverse events classified as mild non-transient symptoms or more severe (see table 9) during CM-OIT (phase 2), in those who have received SLIT pretreatment (group S) compared to the equivalent SLIT dose orally during phase 1 (group O).
- Other safety outcomes in the different treatment groups (withdrawals due to intervention, anaphylaxis rate/adrenaline use)
- Efficacy defined at DBPCFC as the proportion of study participants experiencing:
 - i. No symptoms (or only mild transient symptoms as per table 9) to 8 grams CM protein (approx. 250mls fresh milk) ("Complete desensitisation")
 - ii. No symptoms (or only mild transient symptoms as per table 9) to at least 1.4 grams CM protein (approx. 45mls fresh milk) ("Partial desensitisation")
 - iii. At least a 10-fold increase in eliciting dose (defined as the lowest dose which elicits objective symptoms or signs at challenge).

Efficacy at 6 and 12 months will be compared across all treatment groups (including SLIT pretreatment) vs the equivalent dose administered orally without a sublingual phase (to address hypothesis 2).

- Immunological outcomes (titrated skin prick test, serum IgE) at baseline, 6 and 12 months.
- Change in health-related quality of life (HRQL) measures at 6, 12 and 15 months, as assessed by validated questionnaires (FAQLQ, FAIM, EQ-5D, self-efficacy) in study participants and their parents.

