- iii. The protocol already allows for an assessment for natural resolution of CM allergy, given the inclusion of a control group in Phase 1.

We will use an OIT protocol in Phase 2 that has been adapted from published and unpublished data relating to eliciting doses in children with CM allergy, as well as previous OIT protocols with favourable safety data. All updosings will take place under medical supervision. We therefore expect this protocol to have a satisfactory safety profile, even for those participants randomised to the placebo group in Phase 1.

The efficacy of treatment will be assessed by double-blind, placebo-controlled food challenge (DBPCFC) at the end of each phase, an established research tool in food allergy.⁸ We have chosen a daily maintenance dose of 4000mg CM protein (roughly equivalent to 120 ml or half a cup of milk), on the basis of previous reports that this amount is generally well-tolerated by subjects undergoing OIT on a daily basis, and it is also associated with a suggestion of efficacy. Our main efficacy outcome – "successful desensitization" or ability to tolerate 8000mg CM protein – has been chosen in agreement with previous studies to allow the intake of full milk servings following the intervention. This is expected to allow dietary liberalisation, potentially leading to a positive impact on health-related quality of life.

This is a two centre study: the procedures involved are complex and require intensive clinical assessment only available at specialist allergy centres with experience in food immunotherapy. The study design allows for a more efficient use of resources and promotes consistency in clinical management. The locations (in central London and Madrid) allow for the recruitment of patients from diverse geographical areas and ethnic background.

⁷Jay DC, Nadeau KC. Curr Allergy Asthma Rep. 2014; 14:473.

⁸Plaut M, Sawyer RT, Fenton MJ. Summary of the 2008 NIAID-US FDA Workshop on Food Allergy Clinical Trial Design. J Allergy Clin Immunol 2009;124:671-8.e1.

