4.3. WITHDRAWAL CRITERIA

Subjects will be free to withdraw from the study at any time without affecting their future medical care. Subjects who are withdrawn from active treatment will be invited to remain in the study for assessment of outcome relating to safety and HRQL measures (HRQL will be assessed 3 months after withdrawal).

The safety of study participants is paramount in this study: subjects who are assessed as having had anaphylaxis to a home dose but who do not receive IM adrenaline as per the management plan will have further updosing suspended until the family undergo retraining on the recognition and management of allergic symptoms.

A participant will be withdrawn from the study under the following circumstances:

- If, in the opinion of the study team, compliance with study procedures is suboptimal such that it compromises the patient's safety.
- If, in the opinion of the study team, further participation would adversely affect the participant's health.
- A child develops an exclusion criteria during the updosing phase of the study e.g. a new medication (which would normally be a contra-indication) is commenced.
- If consent is withdrawn or the subject fails to return for a study visit without due reason.

Any subject excluded from further participation will not be replaced, unless withdrawal occurs after initial DBPCFC but prior to allocation to treatment.

⁹Papadopoulos NG, Arakawa H, Carlsen KH, et al. International consensus on (ICON) pediatric asthma. *Allergy*. 2012;67:976-97.

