5.3.2.1. INITIAL ESCALATION DAY

Phase 1 will start with an "escalation day" visit in which up to 7 consecutive doses (starting with 0.01 mg of CM protein) will be given, every 30-60 minutes (Table 4) under medical supervision. Doses will be given either by the sublingual or the oral route according to group allocation.

Participant will be assessed prior to dosing to ensure suitability, as described in section 5.2.1. If a given dose triggers symptoms which cause discomfort to the participant (such as sustained oral itch) or deemed to be significant by the research team, no further doses will be administered on the escalation day.

Participants and/or their family will then be instructed to take the last well-tolerated dose on a daily basis at home, for a minimum of 10 days until the next increase is performed.

PHASE 1 UPDOSING PROTOCOL

Steps	CM protein (mg)	Volume of mix (ml)
Step 1	0.01	0.5
Step 2	0.02	0.5
Step 3	0.04	0.5
Step 4	0.08	0.5
Step 5	0.2	0.5
Step 6	0.4	0.5
Step 7	1	0.5
Step 8	2.5	0.5
Step 9	6	0.5
Step 10	15	0.5
Step 11	30	0.5
Step 12	60	0.5

Table 4: Updosing protocol for phase 1 CM immunotherapy pretreatment

Each step will be administered daily at home for a minimum of 10 days. Once the target dose is achieved (step 12), participants will continue this dose on a daily basis for a target of 16 weeks. The duration of Phase 1 will vary from participant to participant, with the aim of achieving Step 12 within 12 weeks and maintaining Step 12 for 16 weeks. Thus, the duration of Phase will vary from approximately 4 to 7 months, at which time the DBPCFC assessment will be completed and phase 2 intervention commenced.

The starting point in phase 1 (initial dose to be administered on the escalation day) will be individualised based on the outcome of the screening DBPCFC, as shown in Table 5. The NOAEL (No Observed Adverse Event Level or highest dose *not* triggering symptoms) will be used for this purpose, defined as the lowest dose tolerated at DBPCFC excluding transient Grade 1 symptoms (see Table 9).

Tolerated dose (NOAEL) at baseline DBPCFC	Initial dose for Phase 1		Max dose at Initial Escalation day		Max number of doses at initial escalation
	Step	CM Protein (mg)	Step	CM Protein (mg)	
<0.5mg (i.e. symptoms at first dose during DBPCFC)	1	0.01	7	1	7
0.5mg	5	0.2	8	2.5	4
3mg	6	0.4	9	6	4
10mg	8	2.5	10	15	3
30mg	9	6	11	30	3
100mg	10	15	12	60	3
300mg	11	30	12	60	2

Table 5. Starting dose for OIT in Phase 1.

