5.3.3 HOME REACTIONS AND CONSEQUENTIAL CHANGES TO UPDOSING PROTOCOL

In the event of an allergic reaction to a dose of immunotherapy within 2 hours of a dose, either at updosing in hospital or after a dose given at home, the following measures will be taken:

- Families will be instructed to follow their Allergy Management Plan (example in Figure 4), and to contact the study team.
- Where a child is having objective symptoms consistent with possible anaphylaxis (e.g. wheeze, persistent cough, difficulty breathing, stridor or marked swallowing difficulties), families will be instructed to administer the adrenaline auto-injector pen provided and contact the study team on the Emergency number.

Once the study team has been informed, and following complete resolution of symptoms, the following plan of action will be recommended:

- For a single reaction consisting of wheeze, persistent cough, difficulty breathing, stridor or marked swallowing difficulties, the family must not give further doses without contacting the research team. The previous lower dose will be given the next possible day, preferably under medical observation on the Research Unit.
- For mild skin symptoms, itchy mouth, rhinoconjunctivitis or mild abdominal symptoms, reassurance to families will be provided and the current dose will be continued, with daily contact with the study team as needed.
- For persistent reactions for 3+days (within 2 hours of the immunotherapy dose) consisting of abdominal pain, rhinoconjunctivitis or skin symptoms, the local investigator should consider a dose reduction of 50% to be made until symptoms have mostly resolved.
- In the event of other symptoms that prove difficult to the child, the dose can be reduced at investigator's discretion.
- For recurrent symptoms, the local investigator may elect to offer participants an oral antihistamine during Phase 1, prior to dosing, to reduce allergic symptoms to immunotherapy doses, according to accepted clinical practice.

Where a dose reduction is required, the subsequent dose increase should be performed at least 2 weeks later at the Research Unit in hospital under supervision.

In the event of omitted doses:

- If 1-2 days of immunotherapy is missed, the subject can continue with the usual dose.
- If 3-4 days of immunotherapy are missed, the previous dose will be given until the subject can attend the research unit for repeat updosing.

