5.5.2 UPDOSING (PHASE 2)

Updosing in Phase 2 will be performed in a similar manner to that in Phase 1 (section **5.3.2.1**). At each updosing visit, the dose will first be given under medical supervision, followed by observation for at least one hour (2 hours if participant has previously experienced a delayed reaction). Participants will then take that dose daily at home for a minimum of 10 days, until the next updosing visit. Once the target dose is reached (step 16), participants will continue this dose on a daily basis until the final assessment at 1 year has been completed.

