7.2.2 ANALYSIS OF SECONDARY ENDPOINTS

The following secondary analyses will be performed using two-sided testing for non-parametric data at a $p<0.05$ level of significance:

- The incidence of adverse events experienced (including rate of withdrawals, and anaphylaxis/adrenaline use during updosing) between groups S, O and C in phases 1 and 2. Statistical differences will be determined using Fisher's exact test for proportions or using non-parametric tests for graded reactions. Logistic regression will be used to assess the influence of age, gender, asthma status and prior history of anaphylaxis amongst other factors on the incidence of adverse events.
- Efficacy defined at DBPCFC as the proportion of study participants experiencing:
 - No symptoms (or only mild transient symptoms as per table 9) to 8 grams CM protein (approx. 250mls fresh milk) ("Complete desensitisation")
 - No symptoms (or only mild transient symptoms as per table 9) to at least 1.4 grams CM protein (approx. 45mls fresh milk) ("Partial desensitisation")
 - At least a 10-fold increase in eliciting dose (defined as the lowest dose which elicits objective symptoms or signs at challenge)....at 6 and 12 months in the different treatment groups, using a two-sided Fisher's exact test at a $p<0.05$ level of significance.
- This will include a comparison of the efficacy of SLIT compared to the same dose administered orally without a sublingual phase (to address hypothesis 2), and its effect on the subsequent safety of OIT.
 - Immunological outcomes (titrated skin prick test, serum IgE) at baseline, 6 and 12 months.
 - Change in health-related quality of life (HRQL) measures at 6, 12 and 15 months, as assessed by validated questionnaires (FAQLQ, FAIM, EQ-5D) in study participants and their parents.
- Change in health-related quality of life (HRQL) measures at 6, 12 and 15 months, as assessed by validated questionnaires (FAQLQ, FAIM, EQ-5D) in study participants and their parents.
- Immunological outcomes (titrated skin prick test, serum IgE) at baseline, 6 and 12 months.
- The trend in CM-peptide binding over time as well as the potential influence of baseline peptide binding on the outcome of CM-IT will be assessed using a bioinformatics approach as in previous studies.²⁹

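### Section 7.2.2 names anaphylaxis and adrenaline use for analysis only during updosing, although 3.1.2 sets no such limit, so maintenance-dose or home-dose events can drop out of the dedicated comparison

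*Combined protocol and SAP*

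**What the plan says.** Section 3.1.2 lists among the secondary outcomes "Other safety outcomes in the different treatment groups (withdrawals due to intervention, anaphylaxis rate/adrenaline use". No time window or setting is attached.

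Section 7.2.2 is the only analysis text that names this outcome. It plans to compare the incidence of adverse events, "including rate of withdrawals, and anaphylaxis/adrenaline use during updosing) between groups S, O and C in phases 1 and 2", using Fisher's exact test for proportions and non-parametric tests for graded reactions.

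The protocol does not define updosing, and its uses differ:

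- Section 3.2 treats it as a supervised event: "All updosings will take place under medical supervision".
- Section 5.3.3 sets it against home dosing when describing where a reaction may occur: "either at updosing in hospital or after a dose given at home".
- Section 4.3 uses it for a period: "A child develops an exclusion criteria during the updosing phase of the study".

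Both phases include daily dosing at the top dose after the increases end. For phase 1, 5.3.2.1 says "participants will continue this dose on a daily basis for a target of 16 weeks". For phase 2, 5.5.2 says "Once the target dose is reached (step 16), participants will continue this dose on a daily basis until the final assessment".

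**The concern.** The trial asks whether pretreatment makes oral immunotherapy safer, and anaphylaxis and adrenaline use are its named severe-safety measures. If the analyst follows 7.2.2 as written, the comparison reported under that name covers less than the outcome in 3.1.2. A maintenance-phase benefit or harm, or one seen mainly on unsupervised home doses, would not appear in it.

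There is a second issue. The phase 2 starting step is set from the challenge done after phase 1 (5.5.1, Table 7). A window that closes when the increases end therefore depends on the phase 1 result, and may differ in length between arms.

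**Working it through.** The documents give no event rate, power or sample size for this outcome, so there is no stated figure to reproduce. The check compares the texts and then works out exposure from the protocol's own schedule.

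**Inputs**

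- Phase 1 (5.3.2.1): "with the aim of achieving Step 12 within 12 weeks and maintaining Step 12 for 16 weeks".
- Phase 2 length (5.5): 26 weeks, so 26 × 7 = 182 days.
- Time per step: at least 10 days (5.5.2), with visits about every 10–14 days (5.1).
- Top step in phase 2: 16 (Table 6).
- Starting steps in phase 2 (Table 7): 1, 3, 4, 6, 9, 10 or 11. Groups S and O are expected to reach the equivalent of step 10 by the end of phase 1 (5.5).

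**Phase 1, updosing read as a period**

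Maintenance share = 16 / (12 + 16) = 16/28 = 57%. Twelve weeks is the target limit for reaching step 12. A child who gets there sooner spends a larger share on maintenance.

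**Phase 2, updosing read as a period**

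Days to step 16 = (16 − starting step) × 10 to 14. Days outside the window = 182 − that figure.

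| Starting step | Increases | Days to step 16 | Days outside | Share of 182 |
|---|---|---|---|---|
| 9 | 7 | 70–98 | 84–112 | 46–62% |
| 10 | 6 | 60–84 | 98–122 | 54–67% |
| 11 | 5 | 50–70 | 112–132 | 62–73% |

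Starts at steps 1–6 are left out of the table because those children may climb several steps on the escalation day.

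**Phase 2, updosing read as supervised increases**

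From step 10 there are 6 increases plus the first dose, so 7 of 182 dose-days (3.8%) count and about 96% do not.

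**Dependence on arm**

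Each step of difference in starting step changes the period-type window by 10–14 days. For step 9 against step 10 the windows are 70–98 and 60–84 days. Under 3.1.2 as written, every arm has the same planned 182 days.

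**Where the omitted events still count**

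- The overall adverse-event incidence and graded-reaction comparisons in 7.2.2 include them. Table 9 grades severity, and no grade is defined by anaphylaxis or by adrenaline use.
- The primary endpoint (3.1.1, 7.2.1) includes them in phase 2 for groups S and C, and the matching secondary outcome does so for S against O. Both start at mild non-transient symptoms, so an anaphylaxis counts the same as a much milder reaction.

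**The case against.** The strongest reply is that this is loose wording. The list in 7.2.2 is introduced as an inclusion within a wider adverse-event comparison, so it gives examples and does not exclude anything. The closing paragraph of 7.2.2 promises a safety comparison of the sublingual and oral routes with no updosing limit. Anaphylaxis to any study dose is an event of interest (6.1), and all episodes outside challenges go to the IDMC (6.2). The sentence about continuing at step 16 stands under a heading on updosing (5.5.2), and Table 6 applies the word to the whole phase 2 regimen, so a reading that covers maintenance is possible.

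Much of this stands. A reader might infer that maintenance or home anaphylaxis would go uncounted; the documents do not support that, because such events remain in the broader comparisons. Nor do they support saying that every reading of updosing excludes maintenance.

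The reply does not close the gap. The widest reading makes the restriction redundant beside the reference to phases 1 and 2, and it conflicts with the usage in 3.2 and 5.3.3. The closing paragraph of 7.2.2 does not name anaphylaxis or adrenaline, and reporting to the IDMC is not a between-group analysis.

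On arm dependence, a reader might take step 7 as the placebo start and infer a gap of 3 × 10–14 = 30–42 days. No row of Table 7 starts at step 7. Section 5.5 gives it as a level that 90% are expected to tolerate, even after placebo, and 5.5.3 expects most children to start home dosing beyond step 9. A shorter course of increases is also partly a real result of pretreatment, so a lower count would not be wholly artefact.

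**Conclusion.** The inconsistency between 3.1.2 and 7.2.2 is real and should be corrected. On the protocol's usage in 3.2, 4.3 and 5.3.3, the dedicated anaphylaxis and adrenaline comparison omits maintenance-dose events. That is 16 of up to 28 weeks in phase 1, and about 98–122 of 182 days in phase 2 for a step 10 start. On the supervised-visit usage it omits all home-dose events.

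What is lost is the separate comparison of this secondary outcome, because none of the analyses that still count the events isolates it. The direction of the window effect is clear: it tends to be shorter in an arm that benefits from pretreatment. Its size is not; it is about 10–14 days per step of difference, and the documents do not give the starting steps by arm.

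The day counts assume uninterrupted progress at 10–14 days per step. Dose reductions delay the next increase by at least 2 weeks (5.3.3), which shortens maintenance and lowers the omitted share.

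**What to change.** In 7.2.2, delete the words 'during updosing'. State that the comparison counts every anaphylaxis and every adrenaline use after any SLIT or OIT dose, at home or in hospital, in escalation or maintenance, over the whole of each phase, as in 3.1.2. Show splits by updosing or maintenance, and by hospital or home, descriptively. Define updosing for those splits.

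The cost is a wording change and a few table rows. The home diary records doses, symptoms and their timing (5.3.2.1), diary cards record rescue medication (5.5.5), and adverse events go on the CRF (6.2), so no new data are needed. Making the change before unblinding also removes the choice of window from the analyst.

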Improving the safety of oral immunotherapy for cow's milk allergy

(The SOCMA Study)

Version 2.1 dated 11 December 2018

SPONSOR: Imperial College London

FUNDING: J.P. Moulton Charitable Foundation
Sociedad Española de Alergología e Inmunología Clínica (SEAIC)
Sociedad Española de Inmunología Clínica, Alergología y Asma Pediátrica (SEICAP)

STUDY CENTRES: Imperial College London, UK & Niño Jesús Hospital, Madrid, Spain

NRES reference: 18/L0/1070

Protocol authorised by:

Name & Role

Date

Signature

AMENDMENT HISTORY

Amendment No.	Protocol Version	Date issued	Author(s) of changes	Details of Changes made
1	2.1	11 Dec 2018	[name] (CI)	
1. Change in maximum dose in Phase 1 updosing from 70mg to 60mg. Correspondingly, 70mg dose in Phase 2 updosing altered to 60mg.2. Removal of basophil activation test (under mechanistic assessments)3. Addition of [name] as co-PI in Madrid centre4. Minor typos corrected

PROTOCOL SYNOPSIS

Title	Improving the Safety of Oral immunotherapy for Cow's Milk Allergy
Abbreviated title	SOCMA study
Clinical Trials.gov number	NCT02216175
IRAS Number	174513
Sponsor R&D Number	18SM4569
HRA Ethics reference	18/L0/1070
Primary objectives	To evaluate the impact of a sublingual immunotherapy (SLIT) pretreatment on the safety of oral immunotherapy (OIT) in children with persistent IgE-mediated cow's milk (CM) allergy.
Secondary objectives	
1. To evaluate the safety and efficacy of CM-SLIT in children with IgE-mediated CM allergy.2. To assess whether the impact of SLIT pretreatment is dependent on sublingual exposure, or whether the same effect can be achieved through very low dose OIT.3. To evaluate predictors which can identify individuals likely to undergo successful desensitization.4. To assess the impact of CM immunotherapy on health-related quality of life.
Intervention	A two centre, parallel group, three arm, randomised placebo-controlled trial, comparing the safety and efficacy of OIT, with and without pretreatment with sublingual immunotherapy. At the end of each phase, efficacy of treatment will be assessed by double-blind, placebo-controlled food challenge (DBPCFC), to determine the change in threshold of reactivity for each participant.

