5.2.1 CLINICAL ASSESSMENT AND CHECKS PRIOR TO DBPCFC

All subjects will be assessed prior to DBPCFC to determine suitability for a challenge, as follows:

- No intercurrent illness (viral or otherwise)
- No exacerbation in allergic symptoms (eczema, asthma, food allergy) in the preceding week.
- No short-acting β 2 agonists used in the past 12 hours
- No recent antihistamine exposure (e.g. cetirizine, loratadine) in the past 48 hours (72 hours for fexofenadine, 5 days for long-acting antihistamine (e.g. chlorphenamine, desloratadine).
- No oral steroids have been taken in the past 2 weeks
- Baseline observations (temperature, blood pressure, heart and respiratory rate, oxygen saturations, PEFR) within the normal range.
- Baseline physical examination must not reveal any significant acute findings.

Challenges will occur on a Challenge Unit with staff fully trained in the management of allergic reactions including anaphylaxis. Emergency equipment (including oxygen and suction) and medication will be checked beforehand, as per local protocol and international criteria for performance of DBPCFC.

5.2.2 DBPCFC AT BASELINE AND FOLLOWING PHASE 1

The challenge will consist of up to eight incremental doses of CM/placebo given at 20-30 minute intervals, followed by an observation period of 2 hours, as shown in table 2.

Published data indicates that the eliciting dose in milk-allergic patients may be lower than for other food allergens. As a safety measure, during the baseline DBPCFC, the dosing interval between the first (0.5mg) and second (3mg) doses will be extended to 60 minutes. The additional 30 minutes will allow for the detection of symptoms in the most sensitive participants, thus limiting the chance of further but unnecessary CM doses being given.

¹¹Sampson HA, Gerth van Wijk R, Bindslev-Jensen C, et al. Standardizing double-blind, placebo-controlled oral food challenges: AAAAI-EAACI PRACTALL consensus report. J Allergy Clin Immunol. 2012;130:1260-74.

The time intervals following other doses may be extended up to one hour at the local investigator's discretion, where the participant may be experiencing an evolving reaction (as a safety measure, to limit the dose which might in turn moderate the symptoms experienced at challenge).

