For safety reasons, families will be asked to provide their child with a snack to eat one hour after the last dose has been given or the challenge has been stopped due to reaction. Participants will then be observed for a second hour prior to leaving the research unit. This is to avoid the possibility of the participant experiencing further symptoms outside the hospital when eating for the first time after challenge, something which has been noted in previous studies.

Entry and 6 month DBPCFC to Cow's Milk			
Dose	CM protein (mg)	Approximate equivalent volume of fresh CM (ml)	Minimum time interval after dose
1	0.5	0.015	60 mins at baseline DBPCFC, 20-30 mins for 6m DBPCFC
2	3	0.09	20-30 mins
3	10	0.3	20-30 mins
4	30	0.9	20-30 mins
5	100	3	20-30 mins
6	300	9	20-30 mins
7	1000	30	20-30 mins
8	3000	90	2 hours observation
Cumulative dose	4444	~130	
2 hours observation period following last dose to monitor for signs of reaction			

Table 2. Dosing protocol for DBPCFC to CM.

At the second visit of the baseline DBPCFC, the local investigator may elect to give participants who fail to react at either DBPCFC visit a single dose of cow's milk to a cumulative dose of 8 grams (approximately 250ml CM) in an open unblinded manner, 2 hours after the last challenge dose, to confirm tolerance.

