5.6.1 DBPCFC

All subjects will be invited to undergo a further DBPCFC to CM at approximately 12 months as described in 5.2. Both DBPCFC visits should take place between 24-30 weeks after commencing Phase 2 OIT. No OIT dose should be administered on the same day as a challenge visit. The purpose of this challenge is to determine the effect of the treatment in participants' threshold of reactivity. Successful desensitization will be defined as a negative outcome to a cumulative dose of 8g CM protein.

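### Challenge threshold is analysed only as three unadjusted yes/no outcomes; a baseline-adjusted ordinal analysis of the dose step should be added in Section 7.2.2

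*Combined protocol and SAP*

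**What the plan says.** The synopsis and Section 3 give the purpose of the challenge at the end of each phase as "to determine the change in threshold of reactivity for each participant". Section 5.6.1 says the exit challenge is "to determine the effect of the treatment in participants' threshold of reactivity".

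Sections 3.1.2 and 7.2.2 then define efficacy as proportions: "Efficacy defined at DBPCFC as the proportion of study participants experiencing" one of three results. These are no more than mild transient symptoms to 8 g, the same to at least 1.4 g, and "At least a 10-fold increase in eliciting dose (defined as the lowest dose which elicits objective symptoms or signs at challenge". All three are compared at 6 and 12 months "using a two-sided Fisher's exact test at a $p<0.05$ level of significance".

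Section 7.2.2 opens by referring to "two-sided testing for non-parametric data" and provides non-parametric tests for graded reactions. It names no rank, ordinal or other graded analysis of eliciting dose.

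Section 5.3.1 lists threshold among the variables that affect outcome and minimises on eliciting dose. The efficacy tests do not adjust for it.

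**The concern.** Each child is placed on an eight-step ladder at baseline and 6 months and a nine-step ladder at exit. The planned tests keep only which side of a cut-off the child falls on.

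Secondary objective 1 (efficacy of sublingual treatment) and the efficacy part of hypothesis 2 rest on these tests, with about 20 children per arm. Section 1.1 describes the efficacy of sublingual treatment in earlier milk studies as much more limited than that of oral immunotherapy, although this trial uses a higher dose. If the 6-month effect is a moderate gain spread over most children, discarding the step information makes it harder to detect. The data for a graded analysis are already being collected.

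**Working it through.** **1. Inputs from the documents.**
- Table 2 (baseline and 6 months): 0.5, 3, 10, 30, 100, 300, 1000, 3000 mg; cumulative 4444 mg.
- Table 3 (exit): the same eight doses plus 3600 mg; cumulative 8044 mg.
- Entry (Section 4.1): reacts at 1.44 g or less. Doses up to 1000 mg sum to 0.5 + 3 + 10 + 30 + 100 + 300 + 1000 = 1443.5 mg, so a child who first reacts at 1000 mg can enter.
- 22 per arm with 10% loss: 22 × 0.9 = 19.8, about 20 evaluable.
- Efficacy tests: two-sided, 0.05.

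**2. The plan's own figure.** The only sample-size figure is 66, for the primary safety outcome. The continuity-corrected two-proportion formula (70% v 18%, alpha 0.01666, 80% power) gives 22 per arm, or 66, before any loss. Exact Fisher power with 20 evaluable per arm is 78.5% for 70% v 17.5%. No power is stated for any efficacy outcome, so there is none to reproduce.

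**3. What 10-fold means on the ladder.**

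| Baseline dose (mg) | One step up | Two steps up |
|---|---|---|
| 0.5 | 3 (6-fold) | 10 (20-fold) |
| 3 | 10 (3.3-fold) | 30 (10-fold) |
| 10 | 30 (3-fold) | 100 (10-fold) |
| 30 | 100 (3.3-fold) | 300 (10-fold) |
| 100 | 300 (3-fold) | 1000 (10-fold) |
| 300 | 1000 (3.3-fold) | 3000 (10-fold) |
| 1000 | 3000 (3-fold) | none; at exit 3600 (3.6-fold) |

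From 0.5 to 300 mg the cut-off is always two steps. From 1000 mg neither ladder contains a 10-fold higher dose, and the plan gives no scoring rule for that child. Separately, the 6-month ladder stops at 4444 mg cumulative, so it cannot show the 8 g outcome that Section 7.2.2 lists for 6 and 12 months.

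**4. Power if every child shifts (10-fold outcome, 6 months, 20 per arm).** Assumed: baseline log10 threshold mean 1.7, SD 0.9, restricted to reactors at 1000 mg or less; challenge noise SD 0.3; SD of change 0.5 to 0.7; no reaction counted as success. The lower power in each range goes with the larger SD.

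| Mean shift, log10 (active v control) | Fisher, 10-fold | Rank test, change in step | Difference |
|---|---|---|---|
| 0.5 v 0 | 19–27% | 41–58% | 41 − 19 = 22; 58 − 27 = 31 |
| 0.7 v 0.1 | 30–44% | 55–74% | 55 − 30 = 25; 74 − 44 = 30 |
| 1.0 v 0.1 | 63–82% | 87–97% | 87 − 63 = 24; 97 − 82 = 15 |

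Allowing for simulation error and for the baseline-adjusted form, the gain is roughly 14 to 32 points. A wider grid (baseline mean 1.3 to 2.2, SD 0.8; SD of change 0.5 to 1.0; unadjusted rank test) gave 0 to 51 points, median 28.

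**5. Power if only a subset responds.**
- Unadjusted rank test: with 40% gaining 2 log10 and SD of change 0.3, Fisher has 67% and the rank test 59%. A wider grid (30–60% responding) gave −25 to +22 points, median about 1.
- Rank analysis adjusted for baseline step: about −2 to +8 points against Fisher in one set of runs, and about +2 to +15 in another set of ten scenarios. For example, with 40% gaining 2 log10 and SD 0.4, it has 67% and Fisher 61%.

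**6. How much is Fisher rather than dichotomising.** With no true effect, Fisher on the 10-fold outcome rejects in 0.9–1.8% of trials and the rank tests in 3.6–5.1%. An uncorrected Pearson test on the same cut recovers 6 to 14 points in the shift scenarios. On the wider shift grid the median loss falls from 28 to 18 points.

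**The case against.** **The threshold change is analysed.** A reader might infer that change in threshold is ignored. It is not: the 10-fold outcome is a within-child change, it cannot be computed without the baseline dose, and minimisation balances the arms on eliciting dose. What is missing is a graded analysis and covariate adjustment. This objection stands against the stronger reading only.

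**The power loss depends on the model.** A reader might take 14 to 32 points as a property of the plan or of all three outcomes. The documents support neither: they give no threshold distribution and no expected shift, and the range comes from one outcome, at 6 months, with every child shifting. Where only some children respond, an unadjusted rank test can lose to Fisher. That stands against the unadjusted test. The baseline-adjusted analysis stayed within about 2 points of Fisher or did better in the subset scenarios tried, which do not cover every possible mixture.

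**Some of the gain needs no ordinal method.** This is true: a less conservative test on the same cut-off recovers part of it and beats the adjusted rank analysis in most of the subset scenarios. Under shifts the adjusted rank analysis still gains about 6 to 18 points over Pearson.

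**The cut-offs matter clinically.** Section 3.2 names tolerance of 8000 mg as the main efficacy outcome and gives a reason for it, and Section 5.6.2 ties dietary advice to 1.4 g. This stands: the ordinal analysis should sit beside these proportions and not displace them.

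**These are secondary outcomes.** The trial is sized for safety and claims no efficacy power. That limits the weight of the point but is no reason to leave the step data unused.

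**Conclusion.** The point holds in this form: Section 7.2.2 reduces the challenge threshold to three yes/no outcomes tested without adjustment, plans no graded analysis of eliciting dose, and does not use baseline threshold as a covariate.

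Under the assumed inputs in the working, with about 20 children per arm, a baseline-adjusted rank analysis gains roughly 14 to 32 points of power over Fisher on the 10-fold outcome at 6 months if all children shift. If only a subset responds, the difference runs from about −2 to +8 points, up to about +15 in a second set of runs. Part of any gain comes from Fisher's conservatism.

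It does not follow that a real shift would usually be missed. At a shift of 1.0 v 0.1 log10, Fisher itself has 63–82% power. This is a worthwhile improvement to secondary analyses and does not affect the primary safety comparison.

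**What to change.** In Section 7.2.2, add a pre-specified ordinal analysis of the challenge step reached:
- at 6 months on the Table 2 ladder and at 12 months on the Table 3 ladder, with no reaction as the top category of that visit's ladder (the exit ladder has a ninth dose, so the two top categories differ);
- adjusted for baseline step and centre, by rank ANCOVA or proportional odds, with the choice fixed in advance;
- with median step change reported by arm.

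This also places children whose baseline eliciting dose is 1000 mg. Keep the 8 g, 1.4 g and 10-fold proportions as planned, with 8 g remaining the main clinical efficacy outcome.

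The cost is SAP wording and a little programming, with no new data, visits or children. The downside is one more secondary analysis, whose effect measure is less immediate to read than a proportion.
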